7.2.1 Anticipated Adverse Events and Adverse Device Effects

The following complications have been reported for other commercially available Cardiac Mapping Systems (and competitive systems) and are expected to be similar to those anticipated in this registry. Possible anticipated adverse events are including, but not limited to:

- Map shifts without warning or error message
- Complete signal loss of one or more channels
- Pacing malfunction
- Incorrect catheter display
- System freeze/Slow processing
- Electrical shock
- Signal interference
- System shutdown
- Signals duplicated on two separate channels
- Perforation
- Significant signal noise
- Miscellaneous error requiring procedure cancellation
- Loss of data display
- Pacing routed through wrong channel
- Unwanted pacing initiated by the system
- Metal interface
- Bent pins on output cable
- Allergic reaction – Patches
- Temperature too low for ablation
- PIU overheating

The following complications have been reported for commercially available catheters or in published literature and are expected to be similar to those anticipated in this registry. Possible anticipated adverse events are any events associated with any EP procedure including, but not limited to:

- Transient Ischemic Attack (TIA)
- Coronary Sinus dissection or perforation
- Valve damage
- Thrombotic or air embolism
- Hemothorax
- Pericardial effusion
- Unintended complete or incomplete AV, SN or other heart block
- Venous thrombosis
- Endocarditis
- Local tissue reaction
- Death (is result of AE)
- Possible allergic reaction to conscious anesthetic sedation medication or short term exposure to heparin
- Cardiac damage
- Tamponade
- Induced atrial or ventricular arrhythmias
- Pneumothorax
- Myocardial irritability/infarction
- Pleural effusion
- CHF exacerbation or pulmonary edema
- Excessive bleeding
- Infection
- Formation of fibrotic tissue
- Hematoma/seroma
- Vascular perforation or dissection
- Catheter entrapment within the heart or blood vessels
- Atrio-esophageal fistula

These AEs are not unique to catheters being used within the registry and could occur as a result of any EP procedure outside of the registry.

Anticipated non cardiac events are, but not limited to:

- Air embolism
- Cerebral Vascular Accident (CVA)
- Laceration
- Pneumonia
- Pulmonary hypertension
- Respiratory depression
- Anesthesia reaction
- High creatinine phosphokinase
- Phrenic nerve damage
- Pulmonary embolism
- Pseudo-aneurysm
- Sepsis

Clinical Investigational Plan

- Skin burns
- Vasovagal reaction
- Increased risk for somatic and genetic effects
- Syncope
- Acute radiation injury

7.3 Subject Death

7.3.1 Procedure for recording and reporting subject death

Safety surveillance within this registry and the safety reporting, both performed by the investigator, starts at the procedure visit.

In case of a subject death prior to the procedure visit:

- Document the death and any relevant information in the medical records
- Complete a Withdrawal form

All subject deaths (from the time of the Procedure Visit) are to be documented and reported to the sponsor within 72 hours after becoming aware of the event.

Should death occur, the investigator is requested to record death information in the hospital records and immediately document the information on the Death form. By completing the form, the sponsor will be notified.

Patient death is an outcome of a serious adverse event (SAE).

- Death is therefore related to an SAE: all efforts to obtain SAE details should be made and the Adverse Event form must be completed
- The patient's death is an early conclusion of the subject's participation in the registry. Therefore, the investigator is requested to complete the Withdrawal Form.
- The investigator must notify the EC/IRB, if appropriate, in accordance with national and local laws and regulations.

8.0 RISKS AND BENEFITS OF THE REGISTRY

8.1 Description of Subject Population

Up to 500 subjects undergoing EP procedures at centers equipped with EnSite Precision™ Cardiac Mapping System and EnSite Precision™ Software v2.0 will participate in this registry.

8.2 Anticipated Clinical Benefits

The aim of this registry is to collect information on the use and the performance of the EnSite Precision™ Cardiac Mapping System V2.0.

The information collected in this registry will be added to the current knowledge and understanding of treatment options for patients with arrhythmias. Subjects participating in this registry are not expected to experience any additional benefit or harm compared to patients who are not participating in this registry as the registry will follow local standard practice.

8.3 Residual Risks associated with the Device under investigation, as defined in the Risk Analyses Report

The residual risk evaluated in the risk analyses/evaluation documents has been judged acceptable using the criteria defined in the Risk Management Plan and the sponsor's internal policies. The data

Clinical Investigational Plan

obtained and reported in the Risk Management Report, provides sufficient evidence that the EnSite Precision™ Cardiac Mapping System is safe and effective for its intended use.

While steps have been taken to identify risks associated with the system and participation in the registry, there may be risks that are unknown at this time.

8.4 Risks associated with participation in the Registry

Risks to subjects enrolled in this registry include all those risks currently associated with all other commercially available electrophysiology diagnostic procedures and RF catheter ablation procedures. The risks of the procedure are related primarily to mechanical injury to the heart and vessels from catheter manipulation and thermal injury due to RF current delivery, including the risk of thromboembolism and myocardial perforation, especially for ablations in the left atrium.

For those procedures where the physician applies sedation or anesthesia, the standard risks of anesthesia also exist and include allergic reactions, pneumonia, aspiration pneumonitis, atelectasis, prolonged sedation, other medical complications and in very rare cases, death.

This registry does not impose any registry specific procedures, thus does not increase the risk of participating.

8.5 Possible Interactions with concomitant medical Treatments and/or concurrent Medical Interventions

There are no interactions with concomitant medical treatments and/or concurrent medical interventions compared to standard practice.

8.6 Steps that will be taken to control or mitigate the Risks

Every possible effort will be taken to minimize the risks, including:

- Careful selection of experienced investigators who have experience with EnSite Precision™ V2.0 Cardiac Mapping System and study teams for the registry
- Conduction of the ablation procedures in accordance with the IFU of the corresponding devices

8.7 Risk-to-Benefit Rationale

The catheter ablation is a recognized safe and effective treatment of cardiac arrhythmias. The EnSite Precision™ Cardiac Mapping System is believed to not introduce any unanticipated risks compared to current practice, thus benefits outweigh the risks.

9.0 DATA MANAGEMENT

Overall, the Sponsor will be responsible for the data handling.

The sponsor and/or its affiliates will be responsible for compiling and submitting all required reports to governmental agencies.

Data will be analyzed by the Sponsor and may be transferred to the Sponsor's locations outside of Europe and/or any other worldwide regulatory authority in support of a market-approval application.

St. Jude Medical respects and protects personally identifiable information collected or maintained for this clinical trial. The privacy of each subject and confidentiality of his/her information will be preserved

Clinical Investigational Plan

in reports and when publishing any data. Confidentiality of data will be observed by all parties involved at all times throughout the clinical trial. All data will be secured against unauthorized access.

All documents and data will be produced and maintained in a way that assures control and traceability. Where relevant, the accuracy of translations will be guaranteed and documented. All documents, and subsequent versions, related to a clinical investigation will be identifiable, traceable and appropriately stored to provide a complete history of the clinical investigation.

The case report forms will be developed by the Sponsor to capture the data for each subject as required by the CIP. The case report forms will include information on the condition of each subject upon entering, and during the course of, the clinical investigation, exposure to the investigational medical device and any other therapies.

The Principal Investigator or institution will provide direct access to source data during and after the registry for monitoring, audits, EC/IRB review and regulatory authority inspections. As required, the Principal Investigator or institution will obtain permission for direct access to source documents from the subject, hospital administration and national regulatory authorities before starting the registry.

9.1 Data Management Plan (DMP)

A detailed Data Management Plan will be established to ensure consistency of the data. This document will include procedures used for data review, database cleaning, and issuing and resolving data queries. If appropriate, the DMP may be updated throughout the registry duration. All revisions will be tracked and document controlled.

CRF data will be captured in a validated electronic database management system hosted by St. Jude Medical.

Only authorized site personnel will be permitted to enter the CRF data through the electronic data capture (EDC) system deployed by St. Jude Medical. An electronic audit trail will be used to track any subsequent changes of the entered data.

9.2 Document Control and Data Control

9.2.1 Traceability of documents and data

The investigator will ensure accuracy, completeness, legibility and timeliness of the data reported to the sponsor on the CRFs and in all required reports.

9.2.2 Recording data

Source documents will be created and maintained by the investigational site team throughout the registry.

A source document corresponds to the printed, optical or electronic document containing the source data, such as: all clinical records, hospital records, laboratory notes, surgery reports, and any other records that contain the original information of the data required in the registry and in the corresponding adverse event reporting, if any.

To facilitate data collection during the EP procedure, worksheets may be provided to the site where source data can be collected.

The data reported on the CRFs will be derived from, and be consistent with, these source documents, and any discrepancies will be explained in writing.

The CRFs will be validated (eCRF) by the authorized site personnel. An audit trail will be maintained for all corrections.

Clinical Investigational Plan

10.0 MONITORING

Centralized monitoring will occur through routine internal data review. This monitoring is designed to identify missing and inconsistent data, data outliers, and potential protocol deviations that may be indicative of site non-compliance. On-site monitoring may occur at the discretion of the sponsor.

11.0 REGULATORY INSPECTIONS

The investigator and/or delegate should contact St. Jude Medical immediately upon notification of a governmental agency inspection at the site. A clinical monitor or designee will assist the investigator and/or delegate in preparing for the audit.

An investigator who has authority to grant access will permit authorized governmental agency employees, at reasonable times and in reasonable manner, to enter and inspect any establishment where devices are held (including any establishment where devices are used or where records or results are kept).

An investigator, or any person acting on behalf of such a person with respect to the registry, will permit authorized governmental agency employees, at reasonable times and in reasonable manner, to inspect and copy all records relating to the registry.

An investigator will permit authorized governmental agency employees to inspect and copy records that identify subjects, upon notice that governmental agency has reason to suspect that adequate informed consent was not obtained, or that reports required to be submitted by the investigator, to the Sponsor or EC/IRB have not been submitted or are incomplete, inaccurate, false or misleading.

Clinical Investigational Plan

12.0 STATISTICAL CONSIDERATIONS

12.1 Statistical Design, Hypotheses, Method and Analytical Procedures

This is a multi-center, observational, prospective registry. The objective of the registry is to assess and characterize the use and performance of the EnSite Precision™ Cardiac Mapping System and EnSite Precision™ Software v2.0 (The System) in a variety of electrophysiological (EP) procedures and clinical settings.

The endpoints for characterizing and evaluating the objective are as following:

Primary Endpoints:

- EnSite Precision™ Software v2.0 Assessment
 - Accuracy of geometry: Proportion of subjects with accurate geometry
 - Overall system stability: Proportion of subjects with overall system stability
 - Unrecoverable shifts: Proportion of subjects whose map could not be recovered

- Automap™ Module Assessment
 - Mapping time associated with (re-)mapping one or multiple arrhythmias in a single subject with a variety of catheters; mapping time will be summarized (using mean, median, standard deviation, minimum and maximum across arrhythmia types, and for each type of arrhythmia as appropriate) for the following modules:
 - Manual
 - AutoMap™
 - TurboMap™
 - Point density associated with (re-)mapping one or multiple arrhythmias in a single subject with a variety of catheters; mapping points collected and used will be summarized (using mean, median, standard deviation, minimum and maximum across arrhythmia types, and for each type of arrhythmia as appropriate)

Secondary Endpoints:

- EnSite Precision™ Cardiac Mapping System Assessment
 - Ease of Use: Proportion of subjects in whom the mapping system was reported to be excellent, very good, good, poor and N/A
 - Overall Procedure time: will be summarized using mean, median, standard deviation, minimum and maximum

- AutoMark feature Assessment
 - Clinical Utility of the automated RF marker placement: proportion of subjects where the AutoMark feature assisted in identifying gaps in lesion lines
 - Ease of Use of the automated RF marker placement: proportion of subjects where the AutoMark feature was easy to use

Analysis method:

The analysis population will include subjects who have signed the Informed Consent Form and undergone the CIP defined EP study and ablation procedure. Endpoints will be summarized based on available data or measurements in the analysis population, as appropriate.

Clinical Investigational Plan

Data will be categorized and summarized using appropriate descriptive statistics. Continuous data will be summarized using descriptive statistics such as the number of non-missing data, mean, standard deviation and/or median, minimum, or maximum. Categorical data will be summarized using frequency count and its percentage.

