Data Collection	
The use of the EnSite Precision™ Cardiac Mapping System will be assessed by collecting feedback from physicians/operators through specific questions.
 
The performance of the EnSite Precision™ Cardiac Mapping System will be assessed by collecting procedure data and adverse events.

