12.3 Pass/Fail Criteria to be applied to the Results of the Registry

The purpose of this registry is to characterize data collected in the population indicated for a cardiac EP study and/or ablation procedure using a 3D mapping system.

Pass/Fail criteria do not apply to this study.

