12.9 The Treatment of missing, unused or spurious Data, including Drop-outs and Withdrawals

All data available for the endpoints specified among the analysis population will be used as appropriate. No imputation will be used treat missing data.

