12.10 The Exclusion or particular Information for the testing of the hypothesis

Not applicable as hypothesis testing will not be performed.

12.11 The minimum and maximum Number of Subjects to be included for each Center

It is expected to enroll up to 500 subjects in up to 50 centers worldwide. The maximum number of subjects to be included at each enrolling center is 75 (15% of total enrollment) subjects, in an effort to have a balance of the subjects across participating centers. The minimum number of subjects to be included at enrolling centers is 1.

Clinical Investigational Plan

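### The ease-of-use rating for the mapping system offers no grade between good and poor, and the plan does not say whether N/A answers count in the denominator

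*Combined protocol and SAP*

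**What the plan says.** Under the secondary endpoints in section 12.1, ease of use of the mapping system is the "Proportion of subjects in whom the mapping system was reported to be excellent, very good, good, poor and N/A". The Data Collection row of the Synopsis (section 1.0) gives the source in general terms: use of the system "will be assessed by collecting feedback from physicians/operators through specific questions".

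Three statements govern how the answers are summarised:

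- Section 12.1, end of the analysis method: "Categorical data will be summarized using frequency count and its percentage".
- Section 12.1, analysis method: "Endpoints will be summarized based on available data or measurements in the analysis population, as appropriate".
- Section 12.9: "All data available for the endpoints specified among the analysis population will be used as appropriate", with no imputation.

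None of them says when N/A applies, or whether an N/A answer is available data or a missing rating. No section adds a grade between good and poor, and none defines a combined favourable category.

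The analysis is descriptive. Section 12.3 states "Pass/Fail criteria do not apply to this study", and section 12.10 states "Not applicable as hypothesis testing will not be performed". The case report forms are held separately (Appendix G), so the wording of the form item cannot be checked.

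**The concern.** The scale separates three degrees of satisfaction and only one of dissatisfaction. An operator who found the system workable but awkward has no grade that says so, and must round up to good or down to poor. Because the middle grade is never offered, no later analysis can restore it, and reporting all the categories does not help.

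This matters because section 12.1 gives ease of use no comparator, and the plan sets no threshold and no test for it. The distribution of grades is the whole result, so its value depends on what the scale can record. The results are to be submitted for publication (section 17.0), and section 9.0 allows the data to be used in support of a market-approval application.

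The N/A question is a different and smaller one. N/A is not a rating, yet it is listed beside the ratings as a proportion to be reported. Without a stated denominator, the same answers can yield different percentages.

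**Working it through.** The plan states no expected figure for ease of use, so there is nothing to reproduce. Its one derived figure, up to 500 subjects, is 50 / 0.10 = 500 from the ventricular tachycardia rate in section 12.2 and does not bear on this endpoint.

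**Inputs from the plan.** Four rated grades (excellent, very good, good, poor) plus N/A, from section 12.1. Calling the first three favourable and the last unfavourable is the plain meaning of the words; the plan does not classify them.

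**Inputs assumed.** The documents give neither an expected spread of opinion nor an N/A rate. All percentages below are illustrations.

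**Missing middle grade.** Let F, M and P be the true favourable, neutral and unfavourable shares, and let a be the fraction of neutral raters who choose good. Then

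- displayed favourable = F + a × M
- displayed poor = P + (1 − a) × M

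With F = 60%, M = 20%, P = 20%:

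| a | Displayed favourable | Displayed poor |
|---|---|---|
| 0 | 60% | 40% |
| 0.5 | 70% | 30% |
| 1 | 80% | 20% |

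Keeping F at 60%, the displayed favourable range is 60% to 70% if M is 10%, and 60% to 90% if M is 30%. The width of the range equals M.

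The loss is one of identification. A display of 80% favourable and 20% poor arises from true shares of 60/20/20 with a = 1, and equally from 80/0/20. A display of 60% and 40% arises from 60/20/20 with a = 0, and equally from 60/0/40. The reported grades cannot separate these cases.

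**N/A in the denominator.** Let q be the N/A share and r a percentage among actual ratings. If N/A is kept in the denominator, displayed percentage = r × (1 − q). For 90% favourable and 10% poor among raters:

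| q | Factor | Favourable | Poor | Ratio |
|---|---|---|---|---|
| 0% | 1.00 | 90% | 10% | 9:1 |
| 5% | 0.95 | 85.5% | 9.5% | 9:1 |
| 10% | 0.90 | 81% | 9% | 9:1 |
| 20% | 0.80 | 72% | 8% | 9:1 |
| 30% | 0.70 | 63% | 7% | 9:1 |

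The factor is the same for every grade, so the ratio does not move. The effect is also reversible when the N/A count is shown: 81% / 0.90 = 90%. The missing middle grade is not reversible in this way, so the two matters are distinct and the first is the more important.

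**The case against.** The best defence is that nothing in the plan turns on a favourable share. The endpoint is descriptive and secondary, with no pass/fail criterion and no hypothesis test. Section 12.1 names each grade separately and asks for counts with percentages, so a reader can recompute percentages without N/A. The clause allowing available data to be used as appropriate would also let the sponsor exclude N/A. Usability trouble may surface elsewhere too: system stability and unrecoverable shifts are primary endpoints, procedure time is secondary, and section 7.2 requires reporting of all adverse device effects and complaints.

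Most of this stands, and it limits the importance of the point. It does not answer the missing grade: full counts cannot restore a distinction the operator was never able to record, and the other endpoints do not measure operators' opinion of ease of use.

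Four stronger readings are tempting and are not supported:

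- **The result is inflated.** A reader might infer this because 3 of 4 rated grades (75%) are favourable, against 2 of 4 (50%) or 2 of 5 (40%) on balanced scales. Those figures only count response options. They would be expected results only if operators answered at random, and section 8.6 calls for investigators experienced with the system. A middling rater may also choose poor.
- **A good-or-better headline is planned.** No section defines one.
- **The percentages are diluted.** That holds only if N/A occurs and is kept in the denominator. The plan settles neither. Dilution would also lower the favourable share, so it adds nothing to a claim of favourable lean.
- **AutoMark ease of use is a yes/no item on a different scale.** Section 12.1 gives only a summary measure, "proportion of subjects where the AutoMark feature was easy to use". A graded item could be reduced to that for reporting, and the forms are not available to check.

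**Conclusion.** The point holds as a minor one, with moderate confidence. As written, the mapping-system ease-of-use endpoint has no middle grade, so middling opinions are recorded as good or poor and cannot be recovered from the reported distribution. The displayed favourable share can exceed the true one by anything from zero to the full neutral share: 0 to 20 percentage points if 20% of raters are neutral, which is an assumption. The documents support neither a direction nor a size beyond that.

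The N/A matter is an unspecified denominator, not an established error. Its possible effect is a common factor of 0.95 to 0.70 on every rated percentage for assumed N/A shares of 5% to 30%, and none if no N/A occurs.

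Both conclusions assume that the form offers the response options listed in section 12.1. No primary or safety result is affected.

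**What to change.** **If the form can still be changed.** In section 12.1, and on the form item that collects this rating, use a balanced scale with a middle grade. State in 12.1 that percentages are computed over actual ratings only and that the N/A count is reported separately.

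**If the form is already in use.** Keep its grades, exclude N/A from the denominator, give its count separately, report each grade without pooling, and state in the report that no middle grade was offered. This needs no new data.

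**Cost.** One form item and one sentence in 12.1. The downside of changing the scale is that ratings collected before and after the change cannot be pooled, which favours the second option once enrolment is well under way.

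One related matter should be checked at the same time. Section 12.1 counts subjects, while section 5.5 has each physician complete the User Experience Form once. The documents do not say that this form carries the ease-of-use rating. If it does, the unit of analysis also needs to be reconciled.

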5.3 Enrollment Visit

The following enrollment activities will be performed after the subject has been screened including using the screening tool - and found eligible per advice of the tool - and must occur before any registry procedure/visit.

- The principal investigator or delegated study personnel are responsible for screening all potential subjects to determine subject eligibility for the registry
- Record enrollment information (name of the registry, date of consent and Inclusion/exclusion confirmation) in the hospital records and complete and submit the Enrollment form in a timely manner (recommended within 5 days)
- Notification of enrollment to the sponsor will take place when the sponsor receives the enrollment form

If a subject does not meet all inclusion criteria or meets any of the exclusion criteria, the subject cannot participate in the registry, even if they have provided consent, and will not be enrolled.

In case the subject was already consented to participate in the registry, but does not meet inclusion/exclusion criteria, the following actions will be taken.

If registry procedure has not occurred:

- Document enrollment information (name of the registry, date of consent and inclusion/exclusion) in the hospital records; complete the Enrollment and Withdrawal Forms. The form must be authorized / approved by the principal or delegated investigator.
 - o Inform the subject about the withdrawal.
 - o The EC/IRB and CA should be notified appropriately about any deviations with regards to obtaining the informed consent.

If registry procedure has occurred:

- Document enrollment information (name of the registry, date of consent and inclusion/exclusion) in the hospital records; complete the Enrollment and Withdrawal Forms. The form must be authorized / approved by the principal or delegated investigator.
 - o Complete study deviation for inclusion/exclusion not met
 - o The EC/IRB and CA should be notified appropriately about any deviations with regards to obtaining the informed consent.

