5.11 Criteria and Procedures for Subject Withdrawal or Discontinuation

Subjects must be informed about their right to withdraw from the registry at any time and for any reason without sanction, penalty or loss of benefits to which the subject is otherwise entitled and withdrawal from the registry will not jeopardize their future medical care or relationship with the investigator. Subjects will be asked to specify the reason for the Withdrawal, but have the right not to answer.

The investigator may decide to withdraw a subject from the registry at any time with reasonable rationale. The subject's future care will not be influenced by a decision, voluntary or otherwise, to withdraw from the registry. All reasonable efforts should be made to retain the subject in the registry until completion of the registry.

Any withdrawal prior to the procedure (for any reason), should only be documented on a Withdrawal Form.

Reasons for subject's withdrawal include, but are not limited to:

- Subject refuses to continue participation in the registry
- Subject is deceased (cause must be documented)
- Subject's non-compliance
- Subject is 'lost to follow up': Subject does not adhere to the scheduled follow up visits but has not explicitly requested to be withdrawn from the registry. (This does not apply to missed visits). Site personnel should at all times make all reasonable efforts to locate and communicate with the subject in order to achieve subject compliance to the scheduled follow up visits:
 1. A subject will be considered 'Lost to Follow Up' after a minimum of 2 phone calls of a physician or delegate at the site to the subject or contact. These 2 phone calls need to be documented in the subject's hospital records.
 2. If these attempts are unsuccessful, a letter should be sent to the subject's last known address or general practitioner (GP) and a copy of this letter should be maintained in the subject's hospital records.

If a subject withdraws from the registry, the site will record the subject's reasons for withdrawal, on a Withdrawal Case Report Form (CRF).

Clinical Investigational Plan

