12.8 Procedures that take into account all the Data

All subjects who have signed the consent of this registry will be considered enrolled in the study and are eligible for the data summary and analysis. The analysis population will include subjects who have signed the consent form and undergone the CIP defined EP and ablation procedure.

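### Sections 12.1 and 12.8 leave open whether a subject mapped but not ablated is analysed; on one reading, mapping failures that end a case drop out of the primary endpoints

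*Combined protocol and SAP*

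**What the plan says.** The population rule appears twice. Section 12.1 (Analysis method) has: "The analysis population will include subjects who have signed the Informed Consent Form and undergone the CIP defined EP study and ablation procedure". The second sentence of 12.8 has: "The analysis population will include subjects who have signed the consent form and undergone the CIP defined EP and ablation procedure".

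Summaries are tied to that population. Section 12.1 adds: "Endpoints will be summarized based on available data or measurements in the analysis population, as appropriate". Section 12.9 adds: "All data available for the endpoints specified among the analysis population will be used as appropriate", and rules out imputation. Neither brings back a subject who falls outside the set.

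Other places bear on how wide the set is:

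- The first sentence of 12.8 says that everyone who has consented "will be considered enrolled in the study and are eligible for the data summary and analysis".
- Section 12.3 gives the purpose as to "characterize data collected in the population indicated for a cardiac EP study and/or ablation procedure using a 3D mapping system".
- Section 5.3, on consented subjects found ineligible, divides cases only by whether the procedure took place, for example "If registry procedure has not occurred".
- Section 5.11 uses the same dividing line: "Any withdrawal prior to the procedure (for any reason), should only be documented on a Withdrawal Form".

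No section covers a procedure that was begun and then stopped between mapping and ablation.

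**The concern.** The five primary endpoints are accuracy of geometry, overall system stability, unrecoverable shifts, mapping time and point density. All describe mapping. Table 2 in section 5.2 lists mapping and catheter ablation as separate activities of the procedure visit, and section 5.5 asks for fluoroscopy images whenever instability is suspected. Primary endpoint data can therefore exist for a subject who never receives ablation.

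The protocol also foresees how this could happen. The anticipated events in section 7.2.1 include maps that move with no alert, system shutdown, and errors serious enough to cancel the procedure. If the population requires ablation to have been delivered, a mapping failure that ends the case removes itself from the proportions meant to count it. Inclusion would then depend on the outcome being measured.

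At stake are the descriptive primary results. Two analysts could use different denominators for every primary endpoint and both claim to follow the text. Those results are the registry's main product: section 17.0 commits to publication, and section 9.0 allows the data to support a market-approval application.

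**Working it through.** **The plan's own figure.** Section 12.2 wants at least 50 subjects per arrhythmia type and puts ventricular tachycardia (VT) lowest, at 10%: 50 / 0.10 = 500. This reproduces the ceiling. It contains no allowance for enrolled subjects outside the analysis set.

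**Which endpoints need ablation.** None of the five primary definitions in 12.1 refers to it. Among the secondary endpoints, the two AutoMark items concern markers for RF lesions and do depend on it. System ease of use and overall procedure time do not require it by definition.

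**The two readings for a subject mapped and then stopped**

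| Reading of the rule | In the analysis set? |
|---|---|
| One planned procedure, begun | Yes |
| Ablation delivered | No |

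**Bounds on a failure proportion.** Let M be subjects with mapping started, k those not ablated, x failures among the ablated, and f failures among the k. M = 500 is the enrolment ceiling; x, k and f are assumptions, because the documents give none of them.

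- Ablation-delivered reading: x / (M − k)
- All with mapping started: (x + f) / M, which lies between x / M and (x + k) / M

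| x | k | Ablation-delivered reading | All with mapping started |
|---|---|---|---|
| 10 | 5 | 10/495 = 2.02% | 2.0% to 3.0% |
| 10 | 10 | 10/490 = 2.04% | 2.0% to 4.0% |
| 10 | 25 | 10/475 = 2.11% | 2.0% to 7.0% |
| 25 | 5 | 25/495 = 5.05% | 5.0% to 6.0% |
| 25 | 10 | 25/490 = 5.10% | 5.0% to 7.0% |
| 25 | 25 | 25/475 = 5.26% | 5.0% to 10.0% |

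Each stopped case that was a failure adds 1/500 = 0.2 percentage points to the mapping-started figure.

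**Direction.** The two figures agree when f = kx / (M − k). For x = 10 this is 0.10 of 5, 0.20 of 10, or 0.53 of 25. Above that value the ablation-delivered reading understates failures; below it, it overstates them. With f = 0 and x = 10 the overstatement is 0.02, 0.04 or 0.11 points. For proportions counted as success (accurate geometry, stability) the directions reverse.

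**Selection example (assumed inputs).** Suppose 10 of 500 mapped subjects have an unrecoverable shift (2.0%) and 5% of the other 490 are not ablated (24.5).

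- Half of the 10 not ablated: 5 / (500 − 5 − 24.5) = 5/470.5 = 1.1%
- A quarter of the 10 not ablated: 7.5 / (500 − 2.5 − 24.5) = 7.5/473 = 1.6%
- The same 5% among the 10: 9.5/475 = 2.0%, no bias

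**Side effect on VT numbers.** If a share m of subjects, equal across arrhythmias, is mapped but not ablated, expected analysed VT subjects are 500 × 0.10 × (1 − m): 49.0, 47.5 or 45.0 for m = 2%, 5% or 10% (assumed). The exact binomial chance of at least 50 falls from 52% with no exclusions to 46%, 37% or 24%.

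**The case against.** The best reply is that the rule names a single planned procedure. The inclusion criterion in 3.5.1 uses a similar compound term, Table 2 and 5.5 treat it as one visit, and 5.3 and 5.11 ask only whether the procedure occurred. Neither 12.1 nor 12.8 requires completion or RF delivery, and a statement of who is included does not say that nobody else is. On this reading a mapped subject is already in. That is plausible and may be what was intended, but the text does not settle it, and one sentence would.

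A reader might infer that 12.3 and 12.8 contradict the rule outright. That goes too far. Section 12.3 describes patients with an indication, not an analysis set, and the two sentences of 12.8 can be taken as the usual distinction between enrolled and analysed subjects. They add to the uncertainty without amounting to a clear conflict.

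A fair point concerns exposure. Section 5.5 collects images at the start and end of the procedure, so stability and shifts are observed over the whole case. A case stopped early is watched for less time, and counting an uneventful one as stable lowers the failure proportion. The fix has to deal with this.

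Safeguards exist: 3.5 requires all enrolled subjects to be accounted for, 5.5 has the full study exported to the sponsor, and 7.2 requires serious adverse events, adverse device effects and complaints to be reported. These limit hidden loss but do not fix the denominator. The case report forms and Procedure Guidelines are under separate cover, so how stopped cases are recorded cannot be judged here.

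**Conclusion.** The point holds as an unresolved definition. One of two available readings makes inclusion depend on whether the case reached ablation, and hence possibly on a system failure.

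A reader might go further and conclude that the plan excludes mapping failures, or that the reported performance will be flattering. The documents do not support either. The exclusion follows from only one reading, and understatement of failures needs failures to go unablated more often than non-failures. Section 7.2.1 makes that plausible, but no failure or abandonment rate is given. Size and sign are therefore unknown. The upper bounds in the table require every stopped case to be a failure. For mapping time and point density only a loss of valid data is shown, not a bias.

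The harm is confined to descriptive results: 12.10 rules out hypothesis testing and 12.3 sets no pass/fail criterion. It is still worth correcting, because the proportions are the primary result and the mapping-started definition does no harm if the one-procedure reading was meant all along.

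**What to change.** Change the wording of 12.1 and 12.8 as follows:

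- **Primary (software and AutoMap) endpoints and system ease of use:** all consented subjects in whom mapping with the System was started, whether or not ablation followed. Use the outcomes recorded in stopped cases, and count a map lost and not recovered as an unrecoverable shift.
- **Stability and shift proportions:** show them with and without stopped cases, because those cases are observed for less time.
- **Overall procedure time:** report separately for ablated and stopped cases.
- **AutoMark endpoints:** keep the ablated set.
- **Subject flow:** give the numbers consented, mapping started and ablated, with reasons for stopping. This also shows cases cancelled before mapping.
- **Consistency:** reconcile the two sentences of 12.8 and align the wording with 12.3.

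The cost is slightly more reporting and possibly one item on the case report form (mapping started; reason ablation not done) if it is not already captured. No extra subjects or visits are needed, and clinical conduct is unchanged. The performance figures may look less favourable.
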